Appendix C (The IRB-approved Protocol)

G. Consumer Product Classes (To be completed by field technician and participant)

23. Please select use frequency for each product type inside/near your home

	Daily	Weekly	Monthly	Yearly/ Never
Arts and Crafts Products				
Automotive Products				
Home Maintenance				
Cleaning Products				
Personal Care Products				
Pesticides				
Pet Care Products				
Home Office				
Landscape and Yard				

H. Home Observations (To be completed by field technician with input from participant as needed)

24a. Select the answer(s) that best describe the percentage of total floor area in the home.

	0	1-20	21-40	41-60	61-80	81-100
% Covered by carpet or rug						
% Exposed linoleum or linoleum tile						
% Exposed wood or wood laminate						
% Exposed ceramic or stone tile						
% Exposed other						

24b. If a percentage of the floor was "Other," what was the material?

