Appendix C (The IRB-approved Protocol)

4.4.1 Environmental Samples

Additional environmental samples will be collected for analysis of chemicals of interest to EPA. Collection of field samples will be carried out by trained technicians using standardized protocols. A quality assurance project plan (QAPP) and standard operating procedures will be prepared and approved prior to collection of field samples. Field staff will be trained by CDC and EPA personnel. Environmental samples will include indoor air, house dust, soil, and surface wipes.

An indoor air sample will be collected from the main play area in the home. Both passive and active air sample collection will be used. The active air sampling approach will use low volume air samplers placed in a childproof, sound-proof housing and located in the child's play area. The pump flow rate will be sufficiently low to ensure that the pump can run for 5 consecutive days with minimum disruption to the study participants. A polyurethane foam (PUF) filled glass tube will be combined with a quartz or Teflon particle filter for collecting semi-volatile target analytes. Passive air collection will be performed by deploying a sorbent tube diffusion sampler in the child's play area. The passive sampler will collect volatile target analytes. The tube cap will be removed on the first day of sampling, and will be replaced on the return visit on Day 5.

House dust samples will be collected from a floor (preference: carpeted surface; alternate: hard surface) where the children may play or spend time. House dust will be collected using a forensic vacuum equipped with an in-line filter to collect and trap surface dislodgeable particles. The sampled area will be measured, marked, and recorded to ensure accurate documentation of amount of available dust for chemical and biological analyses. If available, field technicians will collect a participant's household vacuum cleaner bag. A swiffer settled dust collection protocol will also be used to collect settled dust from the tops of door jambs and bookcases. Dust samples will also be collected from the aforementioned areas using an electrostatic dust collector (EDC). Two EDCs will be placed horizontally at surfaces at least 1.5 meters above the floor and exposed for five days.

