Appendix C (The IRB-approved Protocol)

Additional questions are designed to address several aspects of the children's dietary habits related to chemical exposures, including information about the number of meals prepared in the home versus elsewhere, exposure-relevant food types (commodities/groups, e.g., dairy, green vegetables, meat), food forms (fresh versus processed), and sources of purchased groceries (e.g., supermarket versus farmer's market).

Finally, the questionnaire includes a number of questions designed to be used in conjunction with the data collected from the housing and community information questions. These include queries about the distance of all locations visited (e.g., parks) from the home, use of outdoor locations at home, the caregiver's perception of the general safety of their children in the locations visited, sleep quality of the child, and the use of public transportation.

The Green Housing Study questionnaires collect considerable information on housing factors. In order to better understand children's exposure factors, additional information will be collected, including technician observations of flooring and furnishings in each room, technician ratings of clutter and cleanliness, and information on the exterior area of the residential complex. The interior metrics will be used to assess the predictability of chemicals in house dust and as additional information for activity-exposure modeling. The exterior metrics (activity areas and surface types) will be used in assessments of child contact with soil, activity-exposure modeling, and the potential for residential track-in of measured chemicals.

Residential location information and selected activity information about the child's interaction with the larger community will be collected. Geospatial location of the residence will be used in the assessment of community attributes for domains that may be important for children's exposure to chemicals and for metrics of potentially important co-exposures and stressors; community-level domains may include pollutant sources such as roads and point sources, walkability, crime/violence, access to parks and food, neighborhood socioeconomic status, and other extant metrics depending on the study location. This information will not be collected through interaction with study participants – it will be obtained from extant data and geodata sources.

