Appendix C (The IRB-approved Protocol)

25a. Select the answer(s) that best describe the home's furniture.

	0	1	2	3	4	5 or more
Number of upholstered sofas						
Number of upholstered chairs						
Number of other upholstered furniture						
Number of twin beds w mattresses						
Number of double beds w mattresses						
Number of queen beds w mattresses						
Number of king beds w mattresses						

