Appendix C (The IRB-approved Protocol)

25b. Select the answer(s) that best describe the percentage of upholstery material for the home's furniture.

	0	1-20	21-40	41-60	61-80	81-100
% Fabric covering						
% Vinyl covering						
% Leather covering						
% Other						

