Appendix C (The IRB-approved Protocol)

I. Indoor Cleanliness (To be completed by field technician)

Whole House Rating for Indoor Residential Cleanliness

26. Select one cleanliness rating for each category, where 1 is low (most clean) and 5 is high (least clean). These ratings apply to the whole house. To be completed by technician observation.

	1 (Low)	2	3	4	5 (High)
Clutter on floor, tables, counters, furniture					
Extent and thickness of dust on surfaces					
Dirt/mold on floor, walls, ceiling					
Peeling interior paint					
Visible pet hair on floor and furniture					
Visible food/crumbs on counters and tables					
Insect/Rodent problem					

27. Select one overall rating of cleanliness for the home. Select a value from a range of 1, Cleanest, to 5, Least Clean.

	1	2	3	4	5	
Cleanest						Least Clean

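### Section 4.5 promises room-by-room flooring and furnishing observations, but the approved form records only whole-home values, so room-level predictors for the floor-dust and play-area air samples cannot be recovered

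*Protocol*

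**What the plan says.** **The promise.** Section 4.5 (Questionnaire) lists, among the additional housing information, "technician observations of flooring and furnishings in each room, technician ratings of clutter and cleanliness". It then gives the purpose: "The interior metrics will be used to assess the predictability of chemicals in house dust". Activity-exposure modeling is named as a second use. The same section names the Appendix C questionnaire as the form on which field staff record home observations.

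**The form.** Parts H and I of that questionnaire contain:
- item 24a, flooring: "Select the answer(s) that best describe the percentage of total floor area in the home", answered in percentage bands;
- item 25a, furniture: "Select the answer(s) that best describe the home's furniture", answered as counts;
- item 25b: "percentage of upholstery material for the home's furniture", again in bands;
- item 26, clutter, dust and dirt: "These ratings apply to the whole house".

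One earlier item is tied to a location. Item 9 (part C) asks whether the floor the child plays on is carpeted, not carpeted or partly carpeted.

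**The samples.** Section 4.4.1 takes technician vacuum dust from one floor where the children may play or spend time, with carpet preferred and a hard surface as the alternative. For air: "An indoor air sample will be collected from the main play area in the home". A household vacuum bag is collected if one is available. Table 7 places the surface wipes in the kitchen and bathroom.

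**The analysis.** Under Objective 1, Section 5.0 regresses analyte measurements on product, activity, location and housing variables to examine their relative contributions to variability in exposure. Table 8 lists house dust and air among the Objective 1 measurements.

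**The concern.** The protocol and its approved form disagree about what technicians will record. If the form is used as it stands, the analyst will know, for example, that 41-60% of a home is carpeted and that it holds two upholstered sofas. The analyst will not know what lies on the floor, or stands in the room, where the dust and air were collected. Banded home totals cannot be split into rooms after the visit.

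A primary objective is affected. Objective 1 asks how much housing factors contribute to variability in exposure, alongside personal factors. Activity and behavior are recorded for each child, whereas flooring type and furnishings would be known only as home-wide summaries. Flooring is also part of the intervention: the renovation components in Appendix A include smooth-surfaced floors and low-VOC carpet.

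**Working it through.** The plan states no figure on this point, so there is none to reproduce. The check compares texts, followed by an illustration on declared assumptions.

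**Step 1. Promise against form.**

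| Feature | Section 4.5 | Appendix C form | Conflict? |
|---|---|---|---|
| Flooring | each room | whole home (24a); carpet on the play floor (item 9) | yes, partly offset |
| Furnishings | each room | whole home (25a, 25b) | yes |
| Clutter and cleanliness | no room stated | whole house (26) | no |

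**Step 2. Is there another instrument?** Tables 3 and 7 list technician-collected housing and community information, but no separate form for it is shown. Table 5a lists procedures GHS-001 to GHS-020, and only GHS-019, the procedure for this questionnaire, names home observation. The procedure for technician-collected dust (GHS-003) is not reproduced. Section 4.4.1 says only that the vacuumed area is measured, marked and recorded.

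**Step 3. Does item 9 close the gap?** Only in part. It has three substantive answers, does not distinguish types of hard floor and says nothing about furniture. It concerns the floor a particular child plays on, and the questionnaire is given for both the index child and the sibling, so one home can yield two different answers. The technician may vacuum any suitable floor where the children spend time and is told to prefer carpet, so the sampled floor need not be the one described.

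**Step 4. What does a whole-home stand-in do?** The documents give neither a room count nor a between-home share of variance. Assume 5 equally weighted rooms, total room variance 1, a share ICC of it between homes, and an outcome that depends only on the sampled room, with slope 1 and residual SD 1.5.
- Covariance of the room value with the home mean = ICC + (1 − ICC)/5, which equals the variance of the home mean. The slope on the home mean is therefore 1. Simulation gave 0.995, 1.005 and 0.997 for ICC 0.2, 0.5 and 0.8. This is Berkson-type error.
- Correlation of the room value with the home mean = √(ICC + (1 − ICC)/5) = √0.36, √0.60 and √0.84 = 0.60, 0.77 and 0.92.
- Correlation with the outcome falls from 1/√(1 + 1.5²) = 0.55 to about 0.33, 0.43 and 0.51 in simulation.

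Correlation and explained variance drop, while the coefficient does not.

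**Step 5. What would that mean for power?** Take n = 64 homes (32 + 32, Section 3.2), two-sided alpha 0.05 and 80% power. The smallest detectable correlation is tanh[(1.960 + 0.842)/√61] = 0.34 when the predictor is measured in the sampled room. With a proxy whose correlation with the room value is k (assumed), the true room-level correlation must be 0.344/k. Power is Φ(√61 · atanh(0.40k) − 1.960) when the true correlation is 0.40.

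| k (assumed) | True r needed | Power at true r = 0.40 |
|---|---|---|
| 1.0 | 0.34 | 91% |
| 0.9 | 0.38 | 84% |
| 0.7 | 0.49 | 61% |
| 0.5 | 0.69 | 35% |

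The range is wide because k is unknown. It shows direction and is not an estimate for this study.

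**The case against.** The strongest reply is that this is a wording mismatch in a pilot. Assessing the suitability of survey variables is itself Objective 2, and the Objective 1 regressions are run only where data suffice. The main flooring contrast, carpet or no carpet, is collected for the play floor in item 9, and item 7 records where the child spends most waking time at home. Several outcomes do not belong to one room: the vacuum bag reflects wherever the household vacuums, and hand wipes, socks and biomarkers follow the child. Whole-home furniture counts may be the better predictor for these. The parent study's home questionnaire, not shown here, also asks about furnishings.

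Much of this stands. It is why the whole-home items should stay and why the point is limited to the technician dust and play-area air samples. It does not reconcile Section 4.5 with items 24a-25b, and it does not supply hard-floor type or furnishings for the sampled room.

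Three stronger readings are tempting but unsupported:
- A reader might infer that the whole-house ratings in item 26 also break a promise. Section 4.5 attaches the room-level wording to flooring and furnishings only.
- A reader might extend the problem to surface wipes and to Objective 5. Section 4.5 names only house dust as the prediction target, and air enters through the Objective 1 regressions. Table 8 does not list surface wipes under Objective 1. Objective 5 relates products, media and biomarkers and names no flooring or furnishing covariate.
- A reader might infer that housing coefficients will be biased toward zero. Step 4 shows that this does not follow when a home average stands in for one of its rooms.

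**Conclusion.** The point holds in limited form. Section 4.5 and the approved form contradict each other on flooring and furnishings, and item 9 offsets this only partly. On the instruments shown, room-level predictors for the technician dust and play-area air samples cannot be recovered after the visit. The likely consequence is lower correlation, explained variance and power for housing factors in Objective 1. Coefficient bias is not established.

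The size cannot be taken from the documents. The figures under steps 4 and 5 depend on an assumed room count, variance split and proxy correlation, and on the outcome depending only on its own room. They should not be quoted as the expected loss or converted into an equivalent number of homes. The conclusion also assumes that no unseen form or dust-sampling field sheet already records the sampled room's floor and furniture.

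**What to change.** Add flooring and furnishing fields (items 24a, 25a and 25b) for the room where floor dust and air are sampled, and name that room on the form. If dust and air come from different rooms, complete the fields for each. The kitchen and bathroom are optional. Keep the whole-home items for use with the household vacuum bag and the personal samples. In the Objective 1 dust and air regressions, state that the sampled room's value is the covariate. Item 26 can stay as it is.

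If room-level items are not added, amend Section 4.5 to describe whole-home metrics and state the limitation for predicting location-specific dust and air samples.

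The cost is a revised technician page, handled as a minor IRB amendment, and a few extra minutes of technician observation per visit. The added fields put no further questions to participants.

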Appendix C (The IRB-approved Protocol)

25a. Select the answer(s) that best describe the home's furniture.

	0	1	2	3	4	5 or more
Number of upholstered sofas						
Number of upholstered chairs						
Number of other upholstered furniture						
Number of twin beds w mattresses						
Number of double beds w mattresses						
Number of queen beds w mattresses						
Number of king beds w mattresses						

Appendix C (The IRB-approved Protocol)

25b. Select the answer(s) that best describe the percentage of upholstery material for the home's furniture.

	0	1-20	21-40	41-60	61-80	81-100
% Fabric covering						
% Vinyl covering						
% Leather covering						
% Other						

Appendix C (The IRB-approved Protocol)

I. Indoor Cleanliness (To be completed by field technician)

Whole House Rating for Indoor Residential Cleanliness

26. Select one cleanliness rating for each category, where 1 is low (most clean) and 5 is high (least clean). These ratings apply to the whole house. To be completed by technician observation.

	1 (Low)	2	3	4	5 (High)
Clutter on floor, tables, counters, furniture					
Extent and thickness of dust on surfaces					
Dirt/mold on floor, walls, ceiling					
Peeling interior paint					
Visible pet hair on floor and furniture					
Visible food/crumbs on counters and tables					
Insect/Rodent problem					

27. Select one overall rating of cleanliness for the home. Select a value from a range of 1, Cleanest, to 5, Least Clean.

	1	2	3	4	5	
Cleanest						Least Clean

Appendix C (The IRB-approved Protocol)

J. Outdoor Housing Information (To be completed by field technician)

28. Residence door is on floor

- Below ground
- Ground
- 2
- 3
- 4
- 5
- 6
- 7
- 8
- 9
- >=10

29. Primary residence door opens to

- Interior Hallway
- Exterior Walkway
- Individual or duplex porch
- Individual or duplex stoop
- Other:

30. Is there a designated playground or play area (not including basketball courts)?

- Yes
- No

Appendix C (The IRB-approved Protocol)

31a. If there is a designated playground or play area, what is the composition of its surface?

	0	1-20	21-40	41-60	61-80	81-100
Grass						
Bare soil						
Natural mulch or bark						
Crumb rubber mulch						
Rubber mats						
Concrete						
Asphalt						
Other						

31b. If "Other" was selected above, please describe the surface.

Appendix C (The IRB-approved Protocol)

APPENDIX D

Considerations for Protection of Human Subjects in the Study

Appendix C (The IRB-approved Protocol)

The U.S. EPA is dedicated to the utmost protection of human subjects who participate in their observational human exposure studies. To ensure the protection of human subjects, the EPA's National Exposure Research Laboratory (NERL) has developed state of the science information to help research scientists address specific elements when developing and implementing their observational human exposure studies. The *Scientific and Ethical Approaches for Observational Exposure Studies* (SEAOES) document developed by NERL (EPA 600/R-08/062, U.S. EPA, National Exposure Research Laboratory, Research Triangle Park, NC, 2008) provides information on regulatory requirements and ethical issues to consider when performing human subjects research. EPA researchers use the information and guidance in the SEAOES document and the *Guidance for Human Subjects Research in the National Exposure Research Laboratory* (EPA 600/R-10/175, U.S. EPA, National Exposure Research Laboratory, Research Triangle Park, NC, 2009) in the design of observational human exposure research studies. The following key elements in the SEAOES document are to be addressed when designing observational exposure research studies: study conceptualization and planning; ensuring protection of vulnerable groups; privacy, confidentiality, and other concerns related to observational human exposure studies; creating an appropriate relationship between the participant and researcher; building and maintaining appropriate community and stakeholder relationships; and designing and implementing strategies for effective communication. These key elements have been addressed by the EPA researchers in this research protocol.

As described in Section 7 of this research protocol, the study will be performed in accordance with human subject protections and procedures in place for the Green Housing Study. The protections and procedures have been developed and implemented at two prior study locations for the Green Housing Study at which the study has already been performed. The CDC Institutional Review Board (CDC IRB) has been responsible for human subject protections for the overall Green Housing Study and will be responsible for review of the human subjects research conducted under this EPA pilot study add-on to the Green Housing Study. The study protocol, consent and assent forms, and the questionnaire will be submitted for review and approval by the CDC IRB. Following CDC IRB approval, the protocol and IRB materials will be submitted to the U.S. EPA Human Subjects Research Review Official (HSRRO) for review and approval. No study recruitment or data collection shall proceed until the CDC IRB and EPA HSRRO approvals are obtained.

The following sections describe Considerations for the Protection of Human Subjects in this research protocol for the EPA pilot study add-on to the Green Housing Study. The considerations address key elements described in the SEAOES document. The elements described below generally follow the outline of the SEAOES document with the intent to highlight the human subject research considerations as related to the information and guidance in SEAOES. Preceding sections of this research protocol are referenced as appropriate.

Appendix C (The IRB-approved Protocol)

1.0 Elements to be considered in study conceptualization and planning

The research protocol for the EPA pilot study add-on to the Green Housing Study details the elements to be considered in study conceptualization and planning.

1.1 Justification for the Proposed Study

The mission of the U.S. Environmental Protection Agency (EPA) is to protect public health and safeguard the environment. The EPA Office of Research and Development's (ORD) Sustainable and Healthy Communities (SHC) Research Program is designed to help decision makers implement environmental management in ways that increase sustainable benefits, such as reducing or eliminating indoor exposures to pollutants from building materials, insecticides, or chemicals found in consumer products. Research conducted in the Enhancing Children's Health project in the SHC program (SHC project 2.2.2) develops the information and methods that decision makers need to assess how the natural and built environments affect children's health and well-being, such as asthma, obesity, and neurocognitive development.

Additionally, EPA ORD's Chemical Safety for Sustainability (CSS) Research Program is developing tools that will use systems approaches to advance the understanding of the links between exposures to chemicals and toxicity pathways that lead to the development of disease. More than 80,000 chemicals are currently listed or registered for use in the U.S. under EPA authorities and at least a thousand more are introduced every year. Many of these chemicals have not been thoroughly evaluated for their potential risks to human health, wildlife and the environment, particularly throughout their life cycle. As a result, a number of important aspects of chemical safety are not adequately understood, including the contribution of exposure to chemicals in the environment to the overall disease burden for susceptible populations. CSS research will dramatically increase the efficiency and speed of chemical evaluations, and will allow EPA to evaluate potential effects of chemical exposures on critical lifestages, such as the embryo and childhood, and other susceptibility factors, including genetics and co-existing diseases.

This EPA pilot study aims to support the needs of both ORD national research programs by addressing how young children's exposures to various indoor pollutants (both chemical and biological agents) change as a result of building renovation-based interventions, potentially affecting their asthma morbidity. This EPA pilot study is an add-on to the Green Housing Study. In addition to supporting EPA research programs, this pilot study will provide additional information on chemical exposures and children's interactions with their environments to enhance ongoing research in the Green Housing Study's evaluation of green housing and impacts on childhood asthma.

